13.3.2.3. Secondary Endpoint Analyses

All secondary endpoints comparisons will be made at the 2-sided 0.05 significance level. Since PFS is the only key secondary endpoint for regulatory registration purposes, no further multiplicity adjustments will be made. Assuming that OS demonstrates significance at the 1-sided 0.025 level, PFS can subsequently be tested at the 2-sided 0.05 level.

PFS

PFS will be analyzed with the methodology specified in Section 13.3.2.1 and Section 13.3.2.2a, c, and d. CCI

ORR and DCR

The treatment comparison for ORR and DCR will be based on the TR population using Fisher's exact test. Treatment estimates and differences will be presented along with the associated 95% CIs.

Time to Deterioration of ECOG Performance Status

Time to deterioration of ECOG performance status to a score of 2 or higher will be analyzed using methodology described in Section 13.3.2.1. Patients not reaching an ECOG of 2 or more (3, 4 or 5) will be censored at the last recorded ECOG assessment.

Quality of Life

Questionnaire compliance rates, for both scales, will be assessed at each measurement time point (baseline, prior to cycle 2, 3, 4, etc.).

Descriptive statistics, for both scales, for the summary scores, as well as the subscale scores will be provided for each assessed time point. In addition, change in QoL scores at representative time points will be determined for the summary, all domains and single items by subtracting each patient's score from their corresponding baseline score. Representative time points will be prior to cycle 2, 3 and 4, chosen based on expected patient compliance to be adequate to allow meaningful analyses, considering the expected treatment duration in the two study groups.

For each domain, the proportion of patients with deteriorating, stable or improving scores prior to cycles 2, 3 and 4 will be compared using Fisher's exact test. In addition, time to QoL deterioration will be evaluated for each arm using Kaplan-Meier estimates and compared using the log-rank test. The criteria for deteriorating, stable or improving scores will be detailed in the SAP.

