4. STUDY DESIGN

4.1. Summary of Study Design

This is a multinational, double-blind, two-arm, parallel, randomized, Phase 3 study evaluating the efficacy and safety of TAS-102 plus BSC versus placebo plus BSC in patients with metastatic gastric cancer who have received at least 2 prior regimens for advanced disease. The study will be conducted under the sponsorship of Taiho Pharmaceutical Co., Ltd. for sites in Japan and Taiho Oncology, Inc. for sites in the rest of the world (ROW).

Eligible patients will be centrally randomized (2:1) to TAS-102 + BSC (experimental arm) or placebo + BSC (control arm) using a dynamic allocation method (biased coin) via an Interactive Voice/Web Response System (IXRS), stratified by:

- Region (ROW1 vs. Japan)
- ECOG PS (0 vs. 1)
- Prior treatment with ramucirumab (yes vs. no)

Study medication should be started within 3 calendar days after the date of randomization and continue until a discontinuation criterion is met or until completion of the primary endpoint analysis, whichever is sooner.

TAS-102 (35 mg/m²/dose) or placebo will be administered orally BID, within 1 hour after completion of morning and evening meals, for 5 days a week with 2 days rest for 2 weeks, followed by a 14-day rest, repeated every 4 weeks [1, 2, 3, 4, 5, 6, 7].

Computed tomography (CT) scans will be performed at baseline and every 8 weeks thereafter until disease progression. On-site tumor assessments will be performed by the Investigator/local radiologist. Tumor assessments will be analyzed using Response Evaluation Criteria in Solid Tumors (RECIST) criteria (Version 1.1, 2009). If patient discontinuation is for reasons other than radiologic disease progression (i.e., with intolerable side effects), patients will be followed every 8 weeks for tumor response until radiologic disease progression or initiation of new anticancer therapy (whichever occurs first).

Quality of life assessments (EORTC QLQ-C30 and QLQ-STO22) will be performed prior to start of dose administration in each cycle.

Flow chart of the Study is presented in the Figure 1.

[figure not shown]

Figure 1. Flow chart of the Study.

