10.4.4.1. ORR

Overall response rate (ORR) is defined as the proportion of patients with objective evidence of CR or PR. The treatment comparison for ORR will be based on the TR population using Fisher's exact test in the subset of patients in the Intent-to-treat population with measurable disease at baseline (TR population). Treatment estimates and differences will be presented along with the associated 2-sided 95% CIs constructed using the Clopper-Pearson approximation to the exact binomial proportion [17] for individual estimates within group; and the normal approximation for the difference between groups.

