10.4.4.2. DCR

Disease control rate (DCR) will be analyzed using the same methodology as that for ORR.

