10.4.4.4.5. Deterioration vs Stable Proportion

For each EORTC QLQ-C30 and QLQ-STO22 score, deterioration in QoL will be defined as a decrease in the score from baseline level of at least five points, the threshold proposed by Osoba et al. [21] as a small but meaningful change in QoL. For each EORTC QLQ-30 and QLQ-STO22 measure, the proportion of patients with deteriorating and (stable or improving) scores at weeks 4, 8 and 12 will be compared using Fisher's exact test. The results will be summarized as a separate table.

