10.4.4.4.6. Time to Deterioration – Main Analysis

Time to first deterioration in QoL (refer to [Section 10.4.4.4.5](#) for definition) will be evaluated for each arm using Kaplan-Meier estimates and compared using the log-rank test (and Cox proportional hazards models adjusting for the baseline value of the EORTC QLQ-C30 and QLQ-STO22 score, country and primary tumour type). Patients with no deterioration in EORTC QLQ-C30 and QLQ-STO22 scores will be censored at the end of study, cut-off date or death date.

CCI

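### DCR and the proportion with QoL deterioration are tested by a valid but mildly conservative unstratified Fisher's exact test that leaves some power unused

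*SAP*

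**What the plan says.** **Tests for the binary endpoints.** SAP 10.4.4.1 sets the method for ORR: "The treatment comparison for ORR will be based on the TR population using Fisher's exact test in the subset of patients" with measurable disease. SAP 10.4.4.2 carries it over: "Disease control rate (DCR) will be analyzed using the same methodology as that for ORR". Protocol 13.3.2.3 agrees: "The treatment comparison for ORR and DCR will be based on the TR population using Fisher's exact test". For QoL, SAP 10.4.4.4.5 states that "deterioration in QoL will be defined as a decrease in the score from baseline level of at least five points", and that the proportions of deteriorating against stable or improving "scores at weeks 4, 8 and 12 will be compared using Fisher's exact test". Protocol 13.3.2.3 also names Fisher's test for QoL, but on three categories before cycles 2, 3 and 4. The visible text gives no stratified or adjusted version of any of these tests.

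**What the other endpoints do.** Randomization is stratified by region, ECOG PS and prior ramucirumab (SAP 4.1). OS is tested by a stratified log-rank test (SAP 10.4.1). PFS (10.4.3) and time to ECOG deterioration (10.4.4.3) take over that method. Time to QoL deterioration (10.4.4.4.6) uses a log-rank test together with "Cox proportional hazards models adjusting for the baseline value of the EORTC QLQ-C30 and QLQ-STO22 score, country and primary tumour type".

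**Status of the endpoints.** SAP 10.4.4 tests the other secondary endpoints at the 2-sided 0.05 level. SAP 10.3 names PFS as the only key secondary endpoint for registration and adjusts no further for multiplicity.

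**The concern.** When allocation is balanced within prognostic strata, an unstratified test counts the between-stratum variation as noise, so it rejects less often than its nominal level allows. Fisher's test is conservative in any case because it is discrete. Both effects cost power.

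For QoL, the chance of falling five points depends on the starting score. Taking the bottom of a scale as zero, a patient who starts below five cannot meet the definition at all. Measuring change from the patient's own baseline does not remove this dependence. The SAP adjusts for baseline in the Cox model but not in the proportion test one section earlier.

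At stake are a few points of power on supportive comparisons in a SAP written to support a marketing application (SAP Section 3). A stratified analysis added after unblinding would be post hoc.

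**Working it through.** **1. The plan's own figure.** The only stated power is for OS: 384 deaths, HR 0.70, 2:1 allocation, 1-sided 0.025 (SAP 4.3.1). By Schoenfeld's formula, √(384 × 2/3 × 1/3) × |ln 0.70| − 1.960 = 9.238 × 0.3567 − 1.960 = 1.335, which is 90.9% power. The stated 90% is reproduced and does not depend on this point. The documents give no rate, effect or power for ORR, DCR or QoL. The one related figure is a DCR of 65.5% in the 29-patient single-arm phase 2 study (protocol 6.1.2.2). All rates, stratum shares, prognostic strengths and evaluable numbers below are therefore assumptions.

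**2. True size of Fisher's test.** Size is the sum of Bin(x; 300, p) × Bin(y; 150, p) over all tables (x, y) with a two-sided Fisher p-value of at most 0.05. At 300:150 it is 3.3% for p = 2%, 4.2% for 10%, 4.4% for 30% and 4.5% for 50%.

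In simulation with 2:1 balance within eight strata and a log-odds effect of 1.0 per factor, Fisher's size is 3.6%, 3.3% and 3.4% at rates of 15%, 30% and 50%. CMH stays at 5.1%, 5.0% and 5.1%.

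**3. DCR power.** With a_k responders on treatment in stratum k, m_k responders in total, and n_1k and n_2k patients per arm (n_k in all), the CMH statistic is [Σ(a_k − n_1k·m_k/n_k)]² / Σ[n_1k·n_2k·m_k(n_k − m_k) / (n_k²(n_k − 1))].

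There were 60,000 simulated trials per row at 300:150, so the Monte Carlo standard error is at most √(0.25/60,000) = 0.2 points. The uncorrected Pearson test separates the two sources of gain: Fisher to Pearson is discreteness, Pearson to CMH is stratification. Gains are taken from unrounded values.

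| Control rate, OR | Log-odds per factor | Fisher % | Pearson % | CMH % | Total gain | From strata |
|---|---|---|---|---|---|---|
| 15%, 2.0 | 0 | 76.3 | 77.8 | 77.8 | 1.5 | −0.1 |
| | 0.5 | 74.4 | 75.9 | 76.6 | 2.2 | 0.7 |
| | 1.0 | 68.2 | 70.0 | 73.2 | 5.0 | 3.3 |
| 30%, 1.8 | 0 | 79.2 | 80.6 | 80.4 | 1.2 | −0.2 |
| | 0.5 | 76.4 | 77.9 | 78.7 | 2.3 | 0.8 |
| | 1.0 | 69.4 | 70.9 | 75.0 | 5.7 | 4.1 |
| 50%, 1.75 | 0 | 76.3 | 79.5 | 79.3 | 3.0 | −0.2 |
| | 0.5 | 73.8 | 77.1 | 78.0 | 4.1 | 0.8 |
| | 1.0 | 66.5 | 70.1 | 74.1 | 7.6 | 4.0 |

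A more specific setting has 290:145 evaluable, 15% Japan, 60% ECOG 1 and 33% prior ramucirumab, with odds ratios for disease control of 0.4 (ECOG 1), 1.5 (Japan) and 0.7 (ramucirumab). With control DCR 20% and treatment OR 1.8, Fisher gives 61.5%, Pearson 63.8% and CMH 65.9%. The gain is 4.4 points, of which 63.8 − 61.5 = 2.3 is discreteness and 65.9 − 63.8 = 2.1 is the strata. Other simulations at this DCR and OR gave 65% to 69% and 63% to 67%. The level varies, but the gain is about 4 points each time.

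**4. QoL proportion.** The assumptions are 220:90 patients, normal scores with mean 60 and SD 22, baseline to follow-up correlation ρ, a mean fall of 6 on placebo, a 7-point benefit, and deterioration as a fall of at least 5. There were 1,500 trials per setting, with a standard error of up to √(0.25/1,500) = 1.3 points for each figure. The logistic model contains treatment and baseline score.

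| ρ | Fisher % | Logistic % | Gain |
|---|---|---|---|
| 0.4 | 42.4 | 53.5 | 11.1 |
| 0.6 | 57.0 | 64.6 | 7.6 |
| 0.8 | 87.5 | 90.6 | 3.1 |

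With no treatment effect the logistic model rejects in 4.3%, 4.9% and 5.1% of trials. A separate simulation gave 45% to 52%, 59% to 66% and 84% to 87%. No Pearson comparator was run here, so part of this gain is also discreteness.

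**5. ORR.** At 2% v about 7.5% with non-prognostic strata, Fisher gives 70.1%, Pearson 73.4% and CMH 73.4%, so the strata add nothing. An exact stratified test, the natural choice with few responses, gives 66.8% against Fisher's 66.6% (2% v 7.4%) and 57.5% against 57.2% (3% v 8.4%).

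**The case against.** The case for leaving the plan alone is strong on several points.

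- **Validity.** Fisher's test keeps type I error at or below 5%, and protocol and SAP agree on it. A reader might infer that ignoring the strata makes the test invalid or biased. It does not; the cost is power only. This stands.
- **Consequence.** No registration decision in the plan rests on these tests, and no planned power is missed because none was stated. This stands.
- **Chance imbalance.** A reader might infer that unadjusted estimates will carry imbalance. Dynamic allocation on the same three factors limits it. The simulations assume balance, so they cannot show this harm. Imbalance within the TR subset is possible but not quantified.
- **QoL.** A reader might infer that the plan ignores baseline for QoL deterioration altogether. It does not: deterioration is measured from the patient's own baseline, and the time-to-deterioration Cox models adjust for the baseline score. The gap is confined to the proportion test. The Cox models do not close it, since they address a different question and omit ECOG PS and prior ramucirumab.
- **Sparse strata.** With the shares above, the smallest of the eight strata (Japan, ECOG 0, prior ramucirumab) holds 0.15 × 0.40 × 0.33 × 435 ≈ 9 patients, about 3 on placebo. Pooling needs a stated rule.

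Redacted text near these sections may hold further analyses. That cannot be settled either way.

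**Conclusion.** The point holds for DCR and for the QoL proportion, as an improvement rather than an error. A typical gain from stratifying DCR is 3 to 4 points of power. The grid above ranges from about 1 point, when the factors do not predict outcome, to about 8, when they predict it strongly.

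It would be tempting to say that the test is conservative because it ignores the strata. That is only partly true. Discreteness accounts for all of the gain when the strata are not prognostic, about half in the specific setting (2.3 of 4.4 points), and between about 28% (1.6 of 5.7) and 48% (3.6 of 7.6) when they are strongly prognostic.

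For the QoL proportion, adjusting for baseline gains about 3 to 11 points, more when the baseline to follow-up correlation is weaker. That rests on unbounded normal scores and a model without the three factors.

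Extending the point to ORR is not supported. Importance is low, because OS, PFS, the alpha-controlled sequence and the sample size are untouched.

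**What to change.** Make these changes before unblinding, as SAP Section 2 requires for analysis decisions.

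- **DCR (SAP 10.4.4.2, protocol 13.3.2.3).** Replace the reference to the ORR method with a CMH test stratified by region, ECOG PS and prior ramucirumab as recorded in IXRS. Report a Mantel-Haenszel risk difference with its 95% CI. State in advance how sparse strata are pooled, for example a minimum stratum size and the order in which factors are dropped.
- **QoL proportion (SAP 10.4.4.4.5, protocol 13.3.2.3).** Use logistic regression of deterioration (yes or no) on treatment, baseline score and the three IXRS factors. Carry the SAP's two-category outcome into the protocol, which has three categories.
- **Fisher's test.** Keep it for both as a sensitivity analysis.
- **ORR (SAP 10.4.4.1).** No change.

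The cost is SAP wording and a few lines of code; baseline scores and strata are already collected. The QoL models number (15 QLQ-C30 + 9 QLQ-STO22 measures) × 3 time points = 72, so name a fallback for models that do not converge.

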6.1.2. TAS-102 in Gastric Cancer

6.1.2.2. Clinical Experience

In a Phase 2 study conducted in Japan (EPOC1201), the efficacy and safety of TAS-102 (35 mg/m² twice daily [BID]) was evaluated in 29 patients with metastatic gastric cancer who had failed standard chemotherapies including fluoropyrimidines, platinum and any of the taxanes or irinotecan.¹ The disease control rate (DCR) was 65.5% (95% confidence interval [CI]: 45.7, 82.1). Median progression free survival (PFS) was 2.9 months and median overall survival (OS) was 8.7 months.

In this population of heavily treated patients, TAS-102 was well tolerated. Common Grade 3 or 4 adverse events (AEs) included neutropenia (69.0%), leukopenia (41.4%), anemia (20.7%) and anorexia (10.3%). Only 2 (6.9%) patients discontinued treatment due to AEs. No treatment-related deaths were observed.

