Objectives: Primary: The primary objective of this study is to evaluate overall survival in patients with refractory metastatic gastric cancer receiving TAS-102 plus BSC or placebo plus BSC Key Secondary: The key secondary objective of this study is to evaluate progression-free survival in patients with refractory metastatic gastric cancer receiving TAS-102 plus BSC or placebo plus BSC. Other Secondary: Other secondary objectives of this study are to evaluate overall response rate, disease control rate, time to deterioration of ECOG performance and quality of life in patients with refractory metastatic gastric cancer receiving TAS-102 plus BSC or placebo plus BSC.		
Methodology: Double blind comparative study (investigational drug vs placebo)		
Number of Subjects (planned and analyzed): Approximately 500 patients will be randomized using a treatment allocation of 2:1 (TAS-102 plus BSC: placebo plus BSC). A target of 384 events (deaths) will be required for the primary analysis.		

Diagnosis and main criteria for inclusion (see protocol Section 2):

Male and female patients age 18 years or older (20 years or older for patients enrolled in Japan) with histologically confirmed, non-resectable, metastatic gastric adenocarcinoma including adenocarcinoma of the gastroesophageal junction, and an ECOG performance status of 0 or 1, who have received at least 2 prior regimens (at least 1 cycle per regimen) for advanced disease, and were refractory to or unable to tolerate their last prior therapy.

- Prior regimens must have included a fluoropyrimidine, platinum, and either a taxane- and/or irinotecan-containing regimen; patients whose tumors are known to be HER2-neu-positive (HER2+) must have received prior anti-HER2+ therapy if available.
- Patients have progressed based on imaging during or within 3 months of the last administration of their last prior regimen.
- Patients who have withdrawn from their last prior regimen due to unacceptable toxicity warranting discontinuation of treatment and precluding retreatment with the same agent prior to progression of disease will also be eligible to enter the study.

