7.3. Tumor Response(TR) Population

The “Tumor Response (TR) Population” will include all patients in the ITT population that meet both of the two following criteria:

1. Subject has measurable disease (at least one target lesion) at baseline;
2. Subject has at least one post-baseline evaluation or early disease progression/cancer-related death occurred before first evaluation on treatment (post-baseline) took place.

All analyses using this population will be based on the treatment assigned by IXRS.

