10.4.4. Other Secondary Efficacy Analysis

All other secondary endpoints comparisons will be made at the 2-sided 0.05 significance level.

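### ORR difference: if response rates are only a few percent, the planned normal-approximation interval can exclude zero when Fisher's test is not significant; a Newcombe interval nearly removes this

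*SAP*

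**What the plan says.** SAP Section 10.4.4.1 prescribes three methods for ORR. The arms are compared with Fisher's exact test in the TR population. The interval within each arm is "constructed using the Clopper-Pearson approximation to the exact binomial proportion". The interval for the difference uses "the normal approximation for the difference between groups". Section 10.4.4.2 applies the same methods to disease control rate (DCR). Section 10.4.4 sets the level: "All other secondary endpoints comparisons will be made at the 2-sided 0.05 significance level".

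Protocol Section 13.3.2.3 plans the same presentation ("Treatment estimates and differences will be presented along with the associated 95% CIs") without naming an interval method.

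On size, the SAP synopsis says "Approximately 500 patients will be randomized using a treatment allocation of 2:1". SAP Section 7.3 limits the TR population to patients who meet, among other conditions, "Subject has measurable disease (at least one target lesion) at baseline". The expected share with measurable disease is not given. No expected ORR is given for either arm. The Phase 2 summary in Protocol Section 6.1.2.2 reports only "The disease control rate (DCR) was 65.5" percent, which is not a response rate.

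**The concern.** The test and the single-arm intervals are exact. Only the interval for the treatment effect rests on a large-sample formula. The Wald formula estimates each arm's variance from its observed proportion, so an arm with no responders contributes no variance at all. With 2:1 allocation, the arm most likely to have 0, 1 or 2 responders is placebo, the smaller one. The lower limit then sits too high, and the error favours TAS-102.

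The practical risk is a table that shows a 95% interval excluding zero beside a non-significant Fisher p-value for the same endpoint. The SAP supports a marketing application (Section 3), so a regulator would be likely to query it. Choosing another interval after the responders are known would look post hoc.

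**Working it through.** **Plan's own figure.** The documents give no ORR rate, power or interval width, so there is nothing on this point to reproduce. The Phase 2 DCR is consistent with 19/29 = 65.5%, and a Clopper-Pearson interval on 19/29 gives 45.7% to 82.1%, as printed in the protocol. It does not inform ORR.

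**Inputs.** From the documents: about 500 patients, 2:1, two-sided 0.05, Fisher's test, normal approximation. Assumed: no continuity correction (none is mentioned); 290 v 145 evaluable, that is 435/500 = 87%; true ORRs as in the table below.

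**Formulas.** With observed proportions p1 = x/n and p2 = y/m, and d = p1 − p2:
- Wald: d ± 1.96 × √[p1(1−p1)/n + p2(1−p2)/m]
- Newcombe, with Wilson limits (l1, u1) and (l2, u2): lower d − √[(p1−l1)² + (u2−p2)²], upper d + √[(u1−p1)² + (p2−l2)²]

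**One outcome by hand: 4/290 v 0/145.** d = 0.0138. The SE is √(0.0138 × 0.9862/290 + 0) = 0.0068. The Wald interval is 0.0004 to 0.0272, which excludes zero. Fisher p = 0.31. The Wilson limits are 0.0054 to 0.0349 and 0 to 0.0258, so the Newcombe lower limit is 0.0138 − √(0.0084² + 0.0258²) = −0.013 and the upper limit is 0.035.

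**Fewest TAS-102 responders at which each method shows a benefit (290 v 145).**

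| Placebo responders | Wald excludes 0 | Fisher p there | Fisher p < 0.05 | Newcombe excludes 0 |
|---|---|---|---|---|
| 0 | 4 | 0.31 | 9 | 9 |
| 1 | 9 | 0.18 | 13 | 13 |
| 2 | 13 | 0.16 | 16 | 16 |

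**Exact enumeration of the binomial outcomes (290 v 145), in percent.** Disagreement means that exactly one of 'interval excludes 0' and 'Fisher p < 0.05' holds.

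| True ORR, TAS-102 v placebo | Wald coverage | Wald lower limit > 0 | Fisher p < 0.05 | Wald–Fisher disagreement | Newcombe coverage | Newcombe–Fisher disagreement |
|---|---|---|---|---|---|---|
| 1 v 1 | 91.5 | 7.8 | 2.4 | 9 | 97.6 | 0.1 |
| 2 v 2 | 92.1 | 6.7 | 3.2 | 7 | 96.3 | 0.4 |
| 3 v 3 | 93.5 | 5.3 | 3.6 | 5 | 96.0 | 0.3 |
| 5 v 5 | 94.6 | 3.9 | 3.9 | 3 | 95.5 | 0.5 |
| 3 v 1 | 95.1 | 43 | 16 | 27 | 97.0 | <0.1 |
| 4 v 1 | 95.4 | 62 | 35 | 26 | 96.8 | 0.1 |
| 4 v 2 | 94.7 | 29 | 14 | 16 | 96.5 | 0.3 |
| 5 v 2 | 95.2 | 45 | 27 | 17 | 96.1 | 1.1 |
| 10 v 2 | 95.1 | 96 | 92 | 4 | 95.9 | 0.6 |

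In the unequal-rate rows, virtually all the disagreement is the Wald interval excluding zero while Fisher p is at least 0.05.

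**Sensitivity to the size of the TR population (333/167, then 200/100).**
- Wald coverage: 91.0% and 94.4% at 1% in both arms; 92.7% and 91.0% at 2%; 93.9% and 92.4% at 3%.
- Disagreement with Fisher: 25% and 31% at 3% v 1%; 14% and 18% at 4% v 2%; 16% and 22% at 5% v 2%; 2% and 11% at 10% v 2%.
- At 2% v 0.5%: coverage 94.2% and 92.0%, disagreement 37% and 34%. In the smaller set the misses there are mostly intervals lying below the true difference.

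**DCR.** At 40% v 30% with 290 v 145, Wald coverage is 94.8% and disagreement 4%.

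**The case against.** The case against giving this much weight has five parts.

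1. *The rates are assumed.* A reader might infer that the documents expect a low ORR. They do not say so. A few percent is plausible for placebo-controlled patients with at least two prior regimens, but it remains an assumption. This stands, and the point is conditional on it.

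2. *Poor coverage and frequent conflict occur in different places.* A reader might take the 16% to 27% disagreement as proof that the interval is wrong. It is not: coverage in those four cells is 94.7% to 95.4% and a true difference exists, so excluding zero is not a false claim. Where coverage fails, at equal rates of 1% to 3%, disagreement is 5% to 9%. This stands.

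3. *Fisher's test is conservative.* Its actual size is 2.4% to 3.6% at equal rates of 1% to 3%, so part of the disagreement comes from the test. This stands for the disagreement. It does not explain the 5.3% to 7.8% false exclusions, which concern the Wald interval alone.

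4. *A normal approximation could carry a continuity correction.* With one, coverage at equal 1% to 2% rates would be about 97% to 99%. The SAP mentions none, so the uncorrected form is the natural reading. The ambiguity is itself a reason to name the method.

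5. *The consequence is limited.* Fisher's test carries the comparison, and the interval is presented beside it. SAP Section 10.3 makes PFS the only key secondary endpoint for registration. This stands.

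**Conclusion.** The point holds conditionally. With about 290 v 145 evaluable patients and an uncorrected Wald interval, two separate things follow.

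- At an ORR of about 1% to 3% in both arms, the interval is too short on the side that favours TAS-102, with false exclusion two to three times the nominal 2.5%.
- At a few percent on TAS-102 and 1% to 2% on placebo, coverage is sound, but the planned table would give conflicting answers in roughly one trial in six to one in four.

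Three broader readings are not supported. The interval is not anti-conservative in general: coverage is 94.6% at 5% in both arms and 95.1% at 10% v 2%. Conflict with Fisher is not frequent at every rate: it is 3% to 4% in those two cells, although it reaches 11% at 10% v 2% if only 300 patients are evaluable. The DCR interval is not defective at mid-range rates.

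This is an inexpensive improvement to an other-secondary endpoint. It does not affect the OS or PFS conclusions.

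**What to change.** In SAP Section 10.4.4.1, replace the normal approximation for the ORR difference with a two-sided 95% Newcombe (Wilson-score) interval, without continuity correction. Keep Fisher's test and the Clopper-Pearson intervals within arms. Record the change in SAP Section 14.

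Miettinen-Nurminen is an acceptable alternative, with coverage of 94.9% to 96.1% in the cells above. It leaves about 2.5% to 6% disagreement with Fisher at 3% v 1%, 4% v 1%, 4% v 2% and 5% v 2%. Newcombe therefore fits better beside Fisher's test.

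Using the same interval for DCR is only for consistency.

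The cost is one phrase and a standard software option, with no extra patients or data. The price is a slightly conservative interval at very low rates (97.6% coverage at 1% in both arms). The change should be made before the database freeze, when SAP Section 2 says analysis decisions are to be settled. If that has passed, report the Newcombe interval beside the planned one and label it as an addition.
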